6.2 Atezolizumab Dose Modification

There will be no dose modifications for Atezolizumab. Adverse events will be managed as described in detail in Appendix “Management of Atezolizumab-Specific Adverse Events”.

If a dose of atezolizumab is withheld for toxicity, then subjects may resume dosing with atezolizumab if that is appropriate at their next scheduled appointment or when toxicity has improved as described in the Appendix “Management of Atezolizumab-Specific Adverse Events”.

Atezolizumab will be withheld for drug-related Grade 4 hematologic toxicities, non-hematological toxicity \geq Grade 3 including laboratory abnormalities, and severe or life-threatening AEs as below and as listed in appendix.

Subjects who require corticosteroids to manage atezolizumab-related AEs must be at an equivalent dose of \leq 10 mg per day of prednisone to resume dosing with atezolizumab. Furthermore, an inability to reduce the corticosteroid dose for managing a drug-related adverse event to the equivalent of \leq 10 mg prednisone per day within 12 weeks of the last atezolizumab dose should prompt discussion between the site investigator and sponsor-investigator regarding the subject’s ability to continue on treatment with atezolizumab the study. With site investigator and sponsor-investigator agreement, subjects with a laboratory adverse event still at Grade 2 after 12 weeks may continue treatment in the study only if asymptomatic and controlled.

In subjects who continue on atezolizumab having experienced a Grade 3, Grade 4, or persistent ($>$ 4 weeks) Grade 2 atezolizumab-related AE, dosing should be held until the AE resolves to Grade 0-1 or baseline.

However, in subjects who experience Grade 3 or 4 pneumonitis, or recurrent persistent ($>$ 4 weeks) Grade 2 drug-related pneumonitis after re-challenge from a prior episode of persistent ($>$ 4 weeks) Grade 2 drug-related pneumonitis, atezolizumab must be permanently discontinued.

For subjects Hepatotoxicity events of Grade 3-4, patients are to permanently discontinue Atezolizumab, with the exception of patients with liver metastasis who began treatment with Grade 2 AST or ALT; if AST or ALT increases by greater than or equal to 50% relative to baseline and lasts for at least 1 week then subjects should be discontinued.

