Subjects with intolerable or persistent Grade 2 drug-related AE may hold study medication at physician discretion. Permanently discontinue study drug for persistent Grade 2 adverse reactions for which treatment with study drug has been held, that do not recover to Grade 0-1 within 12 weeks of the last dose.

Refer to the Atezolizumab Investigator's Brochure for more detailed information regarding dose modification.

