APPENDIX I: MANAGEMENT OF ATEZOLIZUMAB-SPECIFIC ADVERSE EVENTS

Toxicities associated or possibly associated with atezolizumab treatment should be managed according to standard medical practice. Additional tests, such as autoimmune serology or biopsies, should be used to evaluate for a possible immunogenic etiology.

PULMONARY EVENTS

Dyspnea, cough, fatigue, hypoxia, pneumonitis, and pulmonary infiltrates have been associated with the administration of atezolizumab. Patients will be assessed for pulmonary signs and symptoms throughout the study and will also have computed tomography (CT) scans of the chest performed at every tumor assessment. All pulmonary events should be thoroughly evaluated for other commonly reported etiologies such as pneumonia or other infection, lymphangitic carcinomatosis, pulmonary embolism, heart failure, chronic obstructive pulmonary disease, or pulmonary hypertension.

Management Guidelines for Pulmonary Events, Including Pneumonitis

Event	Management
Pulmonary event, Grade 1	
Continue atezolizumab and monitor closely.Re-evaluate on serial imaging.Consider patient referral to pulmonary specialist.Consider withholding atezolizumab
Pulmonary event, Grade 2	
Withhold atezolizumab for up to 12 weeks after event onset.^aRefer patient to pulmonary and infectious disease specialists and consider bronchoscopy or BAL.Initiate treatment with 1–2 mg/kg/day oral prednisone or equivalent.If event resolves to Grade 1 or better, resume atezolizumab.^bIf event does not resolve to Grade 1 or better while withholding atezolizumab, permanently discontinue atezolizumab.For recurrent events, or events with no improvement after 48–72 hours of corticosteroids, treat as a Grade 3 or 4 event.
Pulmonary event, Grade 3 or 4	
Permanently discontinue atezolizumab and contact HCRN.^cBronchoscopy or BAL is recommended.Initiate treatment with 1–2 mg/kg/day IV methylprednisolone.If event does not improve within 48 hours after initiating corticosteroids, consider adding an immunosuppressive agent.If event resolves to Grade 1 or better, taper corticosteroids over \geq 1 month.

BAL = bronchoscopic alveolar lavage.

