^a Atezolizumab may be withheld for a longer period of time (i.e., $>$ 12 weeks after event onset) to allow for corticosteroids (if initiated) to be reduced to \leq 10 mg/day oral prednisone or equivalent. The acceptable length of the extended period of time must be based on assessment of benefit-risk by the investigator and in alignment with the protocol requirement for duration of treatment and documented by the investigator. Sponsor-Investigator is available to advise as needed.

^b If corticosteroids have been initiated, they must be tapered over \geq 1 month to \leq 10 mg/day oral prednisone or equivalent before atezolizumab can be resumed.

^c Resumption of atezolizumab may be considered in patients who are deriving benefit and have fully recovered from the immune-related event. The decision to rechallenge patients with atezolizumab should be based on investigator's assessment of benefit-risk and documented by the investigator (or an appropriate delegate).

Sponsor-Investigator is available to advise as needed

HEPATIC EVENTS

Immune-mediated hepatitis has been associated with the administration of atezolizumab. Eligible patients must have adequate liver function, as manifested by measurements of total bilirubin and hepatic transaminases, and liver function will be monitored throughout study treatment.

Patients with right upper-quadrant abdominal pain and/or unexplained nausea or vomiting should have liver function tests (LFTs) performed immediately and reviewed before administration of the next dose of study drug.

For patients with elevated LFTs, concurrent medication, viral hepatitis, and toxic or neoplastic etiologies should be considered and addressed, as appropriate.

Management Guidelines for Hepatic Events

Event	Management
Hepatic event, Grade 1	
Continue atezolizumab.Monitor LFTs until values resolve to within normal limits.
Hepatic event, Grade 2	
All events:
 
Monitor LFTs more frequently until return to baseline values. 
Events of > 5 days' duration:
 
Withhold atezolizumab for up to 12 weeks after event onset.^aInitiate treatment with 1–2 mg/kg/day oral prednisone or equivalent.If event resolves to Grade 1 or better, resume atezolizumab.^bIf event does not resolve to Grade 1 or better while withholding atezolizumab, permanently discontinue atezolizumab.^c

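### Section 6.2 and Appendix I set different triggers for permanent discontinuation of atezolizumab in Grade 2 pneumonitis, and neither is said to govern

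*Combined protocol and SAP*

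**What the plan says.** **Appendix I, Management Guidelines for Pulmonary Events, Including Pneumonitis.** The Grade 2 row withholds atezolizumab for up to 12 weeks from event onset, extendable by footnote a to allow a steroid taper. It allows resumption once the event is Grade 1 or better and discontinues if that is not reached. Its last instruction covers recurrent events and events without improvement at 48–72 hours on steroids: "hours of corticosteroids, treat as a Grade 3 or 4 event". The Grade 3 or 4 row opens with "Permanently discontinue atezolizumab and contact HCRN". That line carries footnote c: "Resumption of atezolizumab may be considered in patients who are deriving benefit and have fully recovered from the immune-related event". The footnote asks for a documented benefit-risk assessment by the investigator.

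**Section 6.2, Atezolizumab Dose Modification.** For Grade 3, Grade 4 or persistent (more than 4 weeks) Grade 2 related events in subjects who continue, "dosing should be held until the AE resolves to Grade 0-1 or baseline". A pneumonitis rule follows as an exception. It covers Grade 3 or 4 pneumonitis, and a recurrence lasting more than 4 weeks that is "Grade 2 drug-related pneumonitis after re-challenge from a prior episode of persistent" Grade 2 pneumonitis, also of more than 4 weeks. In those cases "atezolizumab must be permanently discontinued". Section 6.2 then leaves holding for an intolerable or persistent Grade 2 event to the physician. It requires permanent discontinuation for held, persistent Grade 2 reactions "that do not recover to Grade 0-1 within 12 weeks of the last dose".

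Section 6.2 refers the reader to the Appendix for adverse event management, but does not say which text prevails where they differ.

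**The concern.** Both texts are operative and both single out pneumonitis, yet they draw the line for permanent discontinuation in different places. A site working from the Appendix table and a site working from the Section 6.2 text could handle the same Grade 2 case differently, each relying on a page of the protocol. The decision at issue is re-exposure after pneumonitis in a lung cancer population, so one such case is enough to matter. Deviation review also lacks a single standard against which to judge the decision.

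**Working it through.** No plan figure has to be reproduced, and no sample size, alpha or event count enters. The check sets the two texts side by side for four kinds of Grade 2 patient.

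| Patient | Appendix I | Section 6.2 | Agreement |
|---|---|---|---|
| A. First episode, no improvement at 48–72 hours on steroids, later recovers to Grade 0–1 within the 12-week limit | Moves to the Grade 3 or 4 row: permanent discontinuation, subject to footnote c | No such trigger; hold, then resumption possible | Differ |
| B. Recurrence, with either episode lasting 4 weeks or less | Same row: permanent discontinuation, subject to footnote c | Recurrence rule not triggered | Differ |
| C. Recurrence, with both episodes lasting more than 4 weeks | Same row: permanent discontinuation, subject to footnote c | Mandatory discontinuation, no exception stated | Both discontinue, but only the Appendix leaves rechallenge open |
| D. Held event that does not resolve by about 12 weeks | Discontinue | Discontinue | Agree in substance; clocks differ |

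**Duration conditions.** For a recurrence, Section 6.2 sets two: more than 4 weeks for the earlier episode and more than 4 weeks for the later one. Appendix I sets none. Row B follows directly.

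**Clocks.** The 48–72 hours run on corticosteroids. The 12 weeks (12 × 7 = 84 days) run from the last atezolizumab dose in Section 6.2 and from event onset in Appendix I. These start at different points, so 2–3 days cannot simply be set against 84. Section 6.4 also ends protocol therapy once it has been interrupted for 63 days or more, so the usable window may be shorter than 84 days. The difference in row A is one of trigger, not a number of days.

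**Route back to treatment.** Even where re-dosing is possible under both texts, the conditions differ. Section 6.2 looks for Grade 0–1 or baseline. Footnote c looks for full recovery, continuing benefit and a documented benefit-risk judgement.

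**How many patients.** The documents give no rate of Grade 2 pneumonitis. Assume 2–5%:

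- 0.02 × 60 = 1.2 patients
- 0.05 × 60 = 3.0 patients

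That counts every patient with any Grade 2 pneumonitis. Only those in rows A to C meet a mismatch, so 1–3 is an upper bound. If half of them did (a further assumption), the count would be 0.5 × 1.2 = 0.6 to 0.5 × 3.0 = 1.5.

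**The case against.** The strongest reply is that Section 6.2 is not a free-standing alternative. It sends adverse event management, resumption and withholding to the Appendix. Its resumption wording is permissive, and it lists cases that must stop without saying that all others must be re-dosed. On that reading Section 6.2 is a minimum and the Appendix supplies organ-specific detail, so a site that applies the wider Appendix trigger breaches nothing. Section 6.1 also gives investigators discretion to modify the guidelines.

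Much of this stands: the two texts are not commands that cannot both be obeyed. It does not close the gap. Section 6.2 states its own pneumonitis rule, as an exception and in mandatory terms. If the Appendix governed, every recurrence would already fall in the discontinuation row and both 4-week qualifiers would do no work. Discretion does not tell a site which rule is the starting point. And the minimum-plus-detail reading fails in row C, where the Appendix is the more permissive text.

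A reader might infer that Section 6.2 never ends treatment for recurrent or non-improving Grade 2 pneumonitis. It does so in rows C and D. A reader might also infer that Appendix I bars these patients outright. It does not, because sending them to the Grade 3 or 4 row brings footnote c with it.

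**Conclusion.** The point holds as a difference in triggers with no stated precedence. The texts direct different handling for a recurrence in which either episode lasted 4 weeks or less, and for a first episode that has not improved at 48–72 hours but later recovers. When both episodes exceed 4 weeks the mismatch reverses: Section 6.2 is absolute and footnote c allows rechallenge.

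The size is small, at most about 1–3 of 60 under the assumed 2–5% rate and probably fewer. The importance lies in safety and in consistency across sites. A reader might infer a threat to the trial's results, but the documents do not support that: the intracranial progression-free survival analysis, the sample size and the futility rule are untouched, and Section 12.6.2 summarises toxicity by type, frequency and severity, with no discontinuation rate among the endpoints. The sponsor should correct it as an internal inconsistency.

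**What to change.** The passages must be reconciled. The sponsor-investigator should state one rule for recurrent and for non-improving Grade 2 pneumonitis, in one place, and have the other passage refer to it. The single statement should settle:

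- what counts as a recurrence, including any minimum duration of either episode;
- whether early lack of response to steroids is a trigger;
- whether footnote c applies to these cases;
- from which date the 12 weeks run, and how that sits with the 63-day limit in Section 6.4.

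A sentence saying which text prevails where Section 6.2 and Appendix I differ would deal with any similar overlaps at the same time. Which clinical rule to adopt is for the sponsor; this review proposes none.

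The cost is a protocol clarification or a short amendment. No procedures, visits or data items are added, and no statistical figure has to be recalculated.
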